12.2.2 Data Submission

The final report will be sent to Zimmer Biomet. The completed database will remain at the hospital and will not be shared with Zimmer Biomet. Copies of the original x-rays taken at the site during the indicated evaluations should be made available to the Sponsor upon request. The original paper source documents, if any, must be kept in a secure location during the course of the study and maintained in accordance with regional and/or national laws/regulations, and EC requirements.

Each party will notify the other party without undue delay upon becoming aware of any Personal Data Breach affecting Patient and /or User Personal Data. The parties will cooperate fully with each other and use commercially reasonable endeavors to assist each other in relation to any reporting or notification obligations in the event of a Personal Data Breach affecting Patient and/or User Personal Data. Further details for handling potential data breach can be found in the respective section in the CTA.

12.2.3 Quality Assurance of Data

The Investigator should ensure the accuracy, completeness, legibility, and timeliness of the data reported to the Sponsor in the final report. Data summarized in the final report should be consistent with the source documents or the discrepancies should be explained.

12.2.4 Patient Privacy and Identification

All patient related data will be kept anonymized and Zimmer Biomet will only receive an anonymized final report..

12.2.5 Data Management

The Investigator and his team is responsible for the data management since the Sponsor only receives an anonymized final report.

12.3 Reporting Requirements

12.3.1 Investigator Reporting Responsibilities

The Investigator should ensure the accuracy, completeness, legibility, and timeliness of data reported to the Sponsor in accordance with this protocol. The Investigator or Designee will provide periodic reports to their EC as required to maintain EC approval throughout the study and will provide any required final reporting to the EC upon study completion/termination. A copy of all EC (re-)approval letters must be submitted to the Sponsor. If the EC terminates or suspends its approval of the study, the Investigator or Designee will suspend study-related activities and will promptly notify the Sponsor. The Investigator should also promptly provide written reports to the Sponsor and the EC regarding any changes significantly affecting the conduct of the study, and/or increasing risk to the subjects.

12.3.2 Retention of Records

Study records must be retained by the Investigator or Designee for a minimum of 15 years from the Investigator's study termination date, or per applicable regulatory and/or EC requirements (whichever time period is greater and allowed by local regulation). Measures shall be taken to prevent accidental or premature destruction.

Study records are defined as all information in original records, certified copies of original records of clinical findings, observations or other activities in a clinical study, including source data initially recorded in an electronic format, necessary for the reconstruction and evaluation of the clinical study. This may include but is not limited to: hospital records, clinic records, laboratory notes, device accountability records, photographs, radiographs, subject casebooks, regulatory records, and all other study-related documents

12.4 Management of Intercurrent Events

12.4.1 Failure to Obtain Informed Consent and/or GDPR notice

Due to the retrospective design of this study, Informed Consent and GDPR consent s not required.

12.4.2 Revision

In the event that removal of one or more of the study related components was necessary, the Investigator has determined the best treatment and/or revision method for the subject. All revision surgeries should be reported as Adverse Events in the final report.

12.4.3 Investigator Withdrawal

Due to the retrospective design of this study, investigator withdrawal is not applicable for this study.

12.4.4 Subject Withdrawal

Due to the retrospective design of this study, subject withdrawal is not applicable for this study.

12.4.5 Lost to Follow-up

Due to the retrospective design of this study, lost to follow-up are not applicable.

12.4.6 Protocol Deviations

The Investigator should not deviate from the agreed upon protocol unless it is to eliminate hazard to the patient. However, any deviation from the protocol has to be documented along with an explanation for the deviation and reported to the Sponsor. Each significant deviation will be reported to the Ethics Committee, if applicable, within the appropriate deadlines stipulated by the appropriate regulatory authorities. Significant deviations are defined as those impacting or potentially impacting patient safety. The Sponsor shall take appropriate corrective and preventative actions to protect the safety of subjects, users, and other persons. Investigator disqualification criteria leading to exclusion from the clinical study include fraud, misconduct and serial non-compliance.

12.4.7 Study Termination

The study terminates after Zimmer Biomet has received and approved the final report. If the Sponsor decides to terminate the study early, the Sponsor will inform the Investigator of the reason for early study termination. It is the responsibility of the Investigator to inform their EC as applicable according to local and national laws/regulations.

12.4.8 Adverse Events

See Safety Management – Medical Events/Adverse Events Section of this protocol for additional information regarding adverse event classifications.

Reporting and Documentation of Adverse Events and Adverse Device Effects

Adverse Events and Adverse Device Effects have to be documented ideally including information on the type of event, date of onset, treatment and resolution, as well as assessment of both the seriousness and the relationship to the study device, instrumentation and/or procedure. Further, the outcome of complications has to be documented and summarized in the final report. In case of early termination of the study, further follow-up of the patient shall proceed according to the hospital's standard procedure.

Reporting and Documentation of Serious Adverse Events, Serious Adverse Device Effects, and Device Deficiencies

Serious Adverse Events and **Serious Adverse Device Effects** have to be **reported to the Sponsor as soon as possible**. The incidence has to be documented over the whole time of the investigation ideally including information on the type of event, date of onset, treatment and resolution, as well as assessment of both the seriousness and the relationship to the study device, instrumentation and/or procedure based on the evaluation of the investigator. The outcome of such complications has to be documented and summarized in the final report. In case of early termination of the study, further follow-up of the study subject shall proceed according to the hospital's standard procedure.

Device Deficiencies that did not lead to an adverse event but **could have led** to a medical occurrence if suitable actions had not been taken, if intervention had not been made or if circumstances had been less fortunate shall be **reported to the Sponsor as soon as possible**, as well.

The **Investigator** is responsible for reporting all SAEs, SADEs, USADEs and Device Deficiencies that could have led to a SADE to the Ethics Committee if required by national regulations or by the EC.

13 Safety Management – Medical Events/Adverse Events

Adverse events are required to be summarized in the final report.. The Investigator or Designee will also promptly provide the Sponsor with any additional requested information required for the Sponsor to comply with regulatory requirements. If applicable per their reporting requirements, the Investigator or Designee will also report applicable adverse event(s) to their EC.

The following definitions are from ISO 14155:2020 [1].

13.1 Classification of the Event

13.1.1 Adverse Event (AE)

Untoward medical occurrence, unintended disease or injury, or untoward clinical signs (including abnormal laboratory findings) in subjects, users or other persons, whether or not related to the investigational medical device and whether anticipated or unanticipated.

Note 1: This definition includes events related to the investigational medical device or the comparator.

Note 2: This definition includes events related to the procedures involved.

Note 3: For users or other persons, this definition is restricted to events related to the use of investigational medical devices or comparators.

13.1.2 Serious Adverse Event (SAE)

A Serious Adverse Event is an adverse event that led to any of the following:

- a. death,
- b. serious deterioration in the health of the subject, users or other persons as defined by one or more of the following:
 1. a life-threatening illness or injury, or
 2. a permanent impairment of a body structure or a body function including chronic diseases, or
 3. in-patient or prolonged hospitalization, or
 4. medical or surgical intervention to prevent life-threatening illness or injury or permanent impairment to a body structure or a body function.
- c. fetal distress, fetal death, a congenital abnormality or birth defect including physical or mental impairment.

Note: Planned hospitalization for a pre-existing condition, or a procedure required by the protocol, without serious deterioration in health, is not considered a serious adverse event.

13.1.3 Serious Health Threat

Signal from any adverse event or device deficiency that indicates an imminent risk of death or a serious deterioration in the health of subjects, users or other persons, and that requires prompt remedial action for other subjects, users or other persons.

Note 1: This would include events that are of significant and unexpected nature such that they become alarming as a potential serious health hazard or possibly of multiple deaths occurring at short intervals.

13.1.4 Adverse Device Effect (ADE)

An Adverse Device Effect is an adverse event related to the use of an investigational medical device.

Note 1: This definition includes adverse events resulting from insufficient or inadequate instructions for use, deployment implantation, installation, or operation, or any malfunction of the medical device.

Note 2: This definition includes any event resulting from use error or from intentional misuse of the medical device.

Note 3: This includes 'comparator' if the comparator is a medical device.

13.1.5 Serious Adverse Device Effect (SADE)

A Serious Adverse Device Effect is an adverse device effect that has resulted in any of the consequences characteristic of a serious adverse event.

13.1.6 Unanticipated Serious Adverse Device Effect (USADE)

An unanticipated adverse device effect is a serious adverse device effect which by its nature, incidence, severity or outcome has not been identified in the current risk assessment.

Note 1: Anticipated serious adverse device effect (ASADE) is an effect which by nature, incidence, severity or outcome has been identified in the risk assessment.

13.1.7 Device Deficiency (DD)

A Device Deficiency is defined as an inadequacy of a medical device with respect to its identity, quality, durability, reliability, usability, safety or performance.

Note 1: Device Deficiencies include malfunctions, use errors, and inadequacy in the information supplied by the manufacturer including labelling.

Note 2: This definition includes device deficiencies related to the investigational medical device or comparator.

It is important to document in the study also all device deficiencies that could have led to a medical occurrence but did not lead to an adverse event.

13.2 Causality Assessment (Relation to Device)

The relationship between the use of the medical device (including the medical - surgical procedure) and the occurrence of each adverse event shall be assessed and categorized. During causality assessment activity, clinical judgement shall be used and the relevant documents, such as the Investigator's Brochure, the Clinical Investigation Plan or the Risk Analysis Report shall be consulted, as all the foreseeable serious adverse events and the potential risks are listed and assessed there. The presence of confounding factors, such as concomitant medication/treatment, the natural history of the underlying disease, other concurrent illness or risk factors shall also be considered.

Each adverse event will be classified according to four different levels of causality:

- Not Related
- Possible (Uncertain)
- Probable
- Causal Relationship (Definitely related)

The Sponsor and the investigators will use the following definitions to assess the relationship of the adverse event to the investigational device, the comparator or the investigation procedure.

13.2.1 Not Related

Relationship to the device, comparator or procedures can be excluded when the event has no temporal relationship with the use of the investigational device, or the procedures related to application of the investigational device.

13.2.2 Possible (Uncertain)

The relationship with the use of the investigational device or comparator, or the relationship with procedures, is weak but cannot be ruled out completely. Alternative causes are also possible (e.g. an underlying or concurrent illness/ clinical condition or/and an effect of another device, drug or treatment). Cases where relatedness cannot be assessed, or no information has been obtained should also be classified as possible.

13.2.3 Probable

The relationship with the use of the investigational device or comparator, or the relationship with procedures, seems relevant and/or the event cannot be reasonably explained by another cause.

13.2.4 Causal Relationship (Definitely related)

The serious adverse event is associated with the investigational device, comparator or with procedures beyond reasonable doubt.

Note: Complications caused by concomitant treatments not imposed by the clinical investigation plan are considered not related. Similarly, several routine diagnostic or patient management procedures are applied to patients regardless of the clinical investigation plan. If routine procedures are not imposed by the clinical investigation plan, complications caused by them are also considered not related.

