10.8.2 Secondary Endpoint

The secondary endpoint is the assessment of safety by recording and analyzing the incidence and frequency of complications and adverse events. Relation of the events to implant, instrumentation and/or procedure should be specified. Subjects' outcomes will also be assessed.

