13.3 Review of Reported Events

The Sponsor will review the investigator's assessment of all reported events submitted to determine and document in writing their seriousness and relationship to the study device and related procedures required by this protocol. In case of disagreement, the sponsor will consult the investigator for clarification and correction if required. If the disagreement cannot be resolved, the Sponsor shall communicate both opinions to the Post Market Surveillance team for further investigation and required reporting if applicable.

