15.1 General

Since all patients have already been operated with the study device and data is only collected retrospectively, there are no anticipated risks specific to study participation. There are no experimental procedures in this study, and participation in this study is not anticipated to affect the medical treatment of included subjects.

When used in accordance with product labelling, the risks associated with the use of the Zimmer Reconstruction System are similar to those of standard, stainless steel systems used for the same

clinical indication or purpose. These risks are either surgical risks or risks associated with the subject procedure/study device. Unanticipated adverse events can also occur.

A list of adverse events (AE) and anticipated adverse device effects (ADE) can be found in the Instruction for Use of the system (see “Adverse Effects” section). Investigators should refer to it.

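### The exclusion in 13.2.4 for care the plan did not impose, and the scope of review in 13.3, do not fit a retrospective study and leave procedure-relatedness open to misgrading (minor)

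*Combined protocol and SAP*

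**What the plan says.** The secondary endpoint (10.8.2) is safety, and it carries an explicit instruction: "Relation of the events to implant, instrumentation and/or procedure should be specified". Sections 11.8, 11.9 and 12.4.8 repeat that request for operative, follow-up and reported events; 11.9 applies it to revisions and implant removals as well.

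Section 13.2 sets four causality levels for each adverse event and treats the surgical procedure as part of using the device. Section 13.2.1 reserves Not Related for events with no link in time to the device or to the procedures by which it is applied.

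Section 13.2.4 defines the top level as follows: "The serious adverse event is associated with the investigational device, comparator or with procedures beyond reasonable doubt". A note then removes two kinds of event from relatedness. The first is concomitant treatment: "Complications caused by concomitant treatments not imposed by the clinical investigation plan are considered not related". The second is routine care, introduced by the remark that "several routine diagnostic or patient management procedures are applied to patients regardless of the clinical investigation plan" and closed by the rule "If routine procedures are not imposed by the clinical investigation plan, complications caused by them are also considered not related".

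Section 13.3 has the sponsor review each event for seriousness and for its "relationship to the study device and related procedures required by this protocol".

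On design, 15.1 begins its risk statement "Since all patients have already been operated with the study device and data is only collected retrospectively" and adds "There are no experimental procedures in this study". Section 11.7 says that the device was used under its IFU and the hospital's usual practice.

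**The concern.** Whether the plan imposed a procedure is a useful test in a prospective investigation, where it separates what the study did to the patient from ordinary care. Here every operation was over before the study began, so everything in the chart is care that the plan did not impose. An assessor who applies the note by its words can place a complication of the index operation, or of a later removal or revision, under Not Related. The sponsor's review in 13.3 uses much the same test, so it is poorly placed to correct the grade.

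What is at stake is the split of adverse events by relation to procedure, which the secondary endpoint asks for. Misgrading would also be hard to see afterwards: under 12.2.1 and 12.2.2 the database stays at the hospital and the sponsor receives an anonymised report, with access to the underlying records only if monitoring takes place (sections 14 and 17).

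**Working it through.** No figure in the plan tests this point, so the check sets the passages side by side.

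1. **Does the plan impose the operation?** No. Section 15.1 says that all patients had already been operated on, and 11.7 places the surgery under the IFU and local practice. The same holds for any removal or revision, which 12.4.2 describes as already decided by the investigator.

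2. **Does the note reach the index operation?** Its two classes are concomitant treatments and routine diagnostic or patient management procedures. Implanting the study device is not plainly either. But the operation was standard care given independently of the plan, and that independence is how the note introduces routine procedures. The wording permits the reading without requiring it.

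3. **Does the note reach removal or revision?** More easily. Section 13.2.1 refers to procedures that apply the device, and taking it out is not clearly one of them. Section 11.9 nevertheless wants revisions and removals linked to implant, instrumentation or procedure.

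4. **Does 13.3 settle it?** No. The protocol requires no operation, so on its words the procedural part of that review has no operation to cover. The device part remains in full.

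5. **Does any passage rank these texts?** No. Sections 10.8.2, 11.9, 13.2 and 13.2.1 point to grading the surgery; 13.2.4 and 13.3 can be read the other way. No sentence exempts the index operation from the note.

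6. **What can change numerically?** Suppose k of the 83 cases have a procedure-related complication and m of those are graded Not Related under the note. The reported procedure-related rate is then (k − m)/83 instead of k/83, a shortfall of m/83. One case is worth 1/83 = 1.2 percentage points. The documents give neither k nor m.

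7. **What cannot change?** The adverse event definition in 13.1.1 applies whether or not an event is related, so totals stand. Under 12.4.2 every revision is reported as an adverse event. The synopsis lists the instruments as part of the study device, and the note excludes no device event. The test in 16.1 concerns fracture healing and uses no relatedness grade.

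8. **A separate mismatch in 13.2.4.** Section 13.2 grades each adverse event on four levels, but the top level is worded only for serious ones. A non-serious event that is definitely related has no level whose wording fits.

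**The case against.** The best reply is that the passages can be read together. Sections 13.2 to 13.2.3, and the opening sentence of 13.2.4, deal with applying the device; the note deals with other care. To treat the index operation as routine patient management would empty the procedure wording of those sections of meaning in this study. The harmonised reading is the more sensible one and is probably what was intended. It stands as a reason to rate the point low. It does not remove the point, because no sentence states it and it covers removal and revision less well than implantation.

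A reader might also infer more than the documents support:

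- *That the note covers any procedure the plan did not impose.* It does not; it is confined to the two classes named above.
- *That instrument-related rates could fall to zero.* Instruments belong to the study device, and device events are outside the note. Section 13.1.4 also counts use error and inadequate implantation instructions as device effects.
- *That the sponsor's review is void.* Section 13.3 still covers all reported events for seriousness and device relationship, and an unresolved disagreement goes to the Post Market Surveillance team with both opinions.
- *That the safety confirmation is unsound, or that a given number of events would vanish.* Totals do not move, no threshold or test depends on the related-event rate, and the documents give no complication count on which to base such a contrast.

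**Conclusion.** The concern holds in a limited form, and it is minor. The note in 13.2.4 and the scope of review in 13.3 rest on a test that a retrospective plan cannot apply, and they conflict with 10.8.2, 11.9, 13.2 and 13.2.1. The result is an unresolved inconsistency that allows complications of the index operation, and especially of a later removal or revision, to be graded Not Related. Procedure-relatedness could then be understated, by an amount that cannot be estimated from the documents.

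This rests on two assumptions: that an assessor may apply the note by its words, and that no guidance outside these documents tells the site otherwise. If assessors follow 13.2 and 13.2.1 throughout, the understatement for the index operation is nil.

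**What to change.** - **13.2.4, note.** Keep it, since it has a proper use for unrelated care, and add a sentence such as: *This note does not apply to the index implantation with its instruments, or to any later removal or revision; complications of these are graded for relatedness under 13.2.*
- **13.3.** Replace the reference to procedures that the protocol requires with the same definition of procedure.
- **13.2.4, definition.** Change *serious adverse event* to *adverse event*, to match 13.2.

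The cost is three wording edits, with no new data. The one downside is that the reported procedure-related rate may be less favourable. Making the change before events are graded avoids regrading.
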